# **Group A Primary Efficacy Endpoint:** Avoidance of intubation at 28 days. **Group A Secondary Efficacy Endpoints:**

- **1.** Final outcome on a 7-point ordinal scale
- **2.** Cardio-circulatory arrest (at any time)
- 3. Renal failure, as measured by RIFLE criteria
- 4. Liver failure, as measured by elevation of ALT and AST to 5x the upper limit of normal or significant worsening of current liver failure with rise in transaminases of >25%
- 5. Evidence of cytokine storm based on measurement of inflammatory markers
- **6.** Type and duration of respiratory support
- 7. Requirement of pressor support
- 8. ICU mortality
- **9.** ICU length of stay
- **10.** In hospital mortality
- **11.** 28-day mortality
- **12.** Length of stay
- **13.** Ventilator-free days
- **14.** Readmission rate
- **15.** Patient level of anti-SARS-CoV-2 IgG at the following times: prior to transfusion, 1-hour post-transfusion, 24 hours post-transfusion, 72 hours post-transfusion, 7 days post-transfusion, every 7 days until discharge, day of discharge.
- **16.** Evaluate the rates, levels (based on CT values) and duration of SARS-CoV-2 RNA in nasopharyngeal swabs using RT-PCR amongst the anti-SARS-CoV-2 convalescent plasma at the following times: prior to transfusion, 24 hours post-transfusion, 72 hours post-transfusion, 7 days post-transfusion, and 14 days post-transfusion.

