#### 2.2 Data collection

The following data points will be gathered for all patients in the study while inpatient. Patients discharged prior to 28 days will receive a phone call to determine their 28 day outcome and patients enrolled in the study will be monitored for 90 days from discharge to determine if there is a readmission and the reason for the readmission.

**COVID-19 Presentation:** Collected on enrollment, see form on page 30.

**Demographics**: Collected on enrollment, see form on page 31.

Medical History: Collected on enrollment, see form on page 31.

Concomitant Medications: Collected on enrollment, see form on page 31.

Vital Signs: Collected daily from enrollment to discharge, see form on pages 30 and 32. Laboratory Values: Collected daily from enrollment to discharge, patient is required to have a CBC with differential, a CMP, a ferritin and a CRP. On enrollment and weekly the patient must have an IL-6, D-Dimer, procalcitonin, LDH, fibrinogen, ESR, and CK. IL-6 and LDH, other laboratory values will be recorded when obtained through standard of care. See form on page 32.

Clinical Status: Collected daily from enrollment to discharge, see form on page 32.

**Medications:** Collected daily from enrollment to discharge, see form on page 33.

Serology Values: Collected per schedule, see form on pages 34 and 35.

PCR Values: Collected per schedule, see form on page 36

Safety Data: Collected for first 24 hours after transfusion, see form on page 37.

**Outcomes:** Collected at discharge or death, see form on pages 38 and 39.

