**Secondary Outcomes:** Analyses of all secondary outcomes will use a 0.3% significance level based on the Bonferroni correction for 16 tests. Final outcome measured on a 7-point ordinal scale will be analyzed using standard linear regression,

although we will also consider proportional odds models should the range of the scale actually used be small (i.e., only 3-4 categories appear in the data). We will not use splines for the standard linear regression, but will use splines if a proportional odds model is fit to the data. We will use the same logistic regression approach as for the primary outcomes for all binary secondary outcomes (cardio-circulatory arrest, renal failure, liver failure, evidence of cytokine storm, pressor support required, and readmission).

We anticipate a small number of total number of mortality events for Group A. Should mortality for Group A be small, we will use Fisher's exact test based on categorizing the unit received by each patient as either low vs. high for amount of Anti-SARS-CoV-2-spike protein IgG. The cutoff for categorizing units will be based on either median amount or based on the cutoff determined by the Bayesian log-binomial piecewise model. For Group B, all secondary mortality outcomes will be analyzed the same as for the primary outcome. Should the number of events for any specific type of mortality (e.g., ICU mortality) prove small, we will use the approach used for analyses of Group A.

We will use a generalized linear model with splines to analyze all duration types of variables (duration of respiratory support, ICU length of stay, total length of stay). We will consider using normal, log-normal, and gamma distributions, along with appropriate links.

Type of respiratory support will be analyzed using a multinomial regression with splines for antibody amount, although we will also consider using Fisher's exact test by categorizing the unit received by each patient as either low vs. high for amount of Anti-SARS-CoV-2-spike protein IgG.

We will use either standard linear regression or Poisson regression for ventilator-free days, including splines.

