We will use generalized linear mixed models to characterize changes in patient level of anti-SARS-CoV-2 IgG, and the rates, levels (based on CT values) and duration of SARS-CoV-2 RNA in nasopharyngeal swabs. These models will include time as a fixed effect, and will also include the random intercept for subject. We will also consider adding other random coefficients based on both AIC and BIC.

**Investigational Outcomes:** We will examine the relationship between primary and appropriate secondary outcomes with IgA levels as an investigational analysis using the same types of models being fit as for IgG levels.

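### Viral RNA duration and CT level are assigned to mixed models that do not handle censored clearance times, negative swabs, or loss of swabs to discharge and death

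*Combined protocol and SAP*

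**What the plan says.** Secondary endpoint 16 in both groups (Section 2.1) covers the presence, level and persistence of viral RNA, with swabs "prior to transfusion, 24 hours post-transfusion, 72 hours post-transfusion, 7 days post-transfusion, and 14 days post-transfusion". The schedule in Section 2.4 shows RT-PCR at the same times and none later.

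Section 2.2 states: "The following data points will be gathered for all patients in the study while inpatient". After discharge, "Patients discharged prior to 28 days will receive a phone call to determine their 28 day outcome", and readmission is tracked; no post-discharge swab is described. It also says "PCR Values: Collected per schedule, see form on page 36". That form has a result field and a CT field for each scheduled time, with no instruction on the CT of a negative swab. Footnote g of Section 2.4 says that listed laboratory tests done in routine care will be tracked, and RT-PCR is on that list.

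Section 3.1 sends "the rates, levels (based on CT values) and duration of SARS-CoV-2 RNA in nasopharyngeal swabs" to generalized linear mixed models and adds: "These models will include time as a fixed effect, and will also include the random intercept for subject". Neither unit IgG nor an IgG-by-time term is named. The same section says "We will use a generalized linear model with splines to analyze all duration types of variables", but the variables it lists there are respiratory support and lengths of stay, not RNA, and censoring is not mentioned. RNA duration is not defined anywhere. No rule covers a patient who is still positive at the last swab, at discharge or at death.

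**The concern.** Three features of the data do not fit the stated model.

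- Duration is one value per patient. A model with time as a covariate and a random intercept per patient has no repeated duration outcome to fit.
- Duration is never observed exactly. It lies between two swabs, or beyond the last one. Death ends observation in a different way from discharge, because a patient who has died cannot clear later.
- A negative swab has no CT value. The analyst must drop it, which removes the patients who cleared, or invent a number for it.

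Endpoint 16 is the only endpoint that measures the virus directly, in a trial whose aim is to relate antibody amount to effect. An avoidable distortion here could hide an antiviral effect or create one.

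**Working it through.** The plan gives no effect size, CT distribution, detection limit, length of stay or power for viral RNA, so there is no figure of its own to reproduce. The only design number that applies is the secondary significance level: 0.05/16 = 0.003125, printed as 0.3%, which is a two-sided |z| of about 2.97.

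**Structure.** Swab days 0, 1, 3, 7 and 14 leave gaps of 1, 2, 4 and 7 days. Clearance is known only to fall in one of these gaps, or after the last swab. Section 3.2 assumes 25% baseline 28-day survival in Group B, so 1 - 0.25 = 75% are assumed to die by day 28. The documents do not say how many die by day 14.

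**Simulation 1 (all inputs assumed).** n = 300, 12 replicates per setting, protocol swab days. Baseline CT has mean 28 (SD 4) and rises 0.9 per day (SD 0.3), with residual SD 2; a swab is negative from CT 40. The IgG effect is +0.15 CT/day per SD, or zero. Inpatient time is 2 + exponential (mean 12) days. The average patient reaches CT 40 at (40 - 28)/0.9 = 13.3 days. So even with everyone kept in hospital, 47% had no observed clearance by day 14; with discharge it was 75-83%.

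CT columns give the slope effect per SD of IgG, with attenuation in brackets, = 1 - estimate/complete-data estimate. Duration columns give log-duration per SD of IgG.

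| Leaving hospital | CT, complete data | Positive swabs only | Negatives set to 40 | Duration, true | Last positive day, uncensored | Interval-censored log-normal |
|---|---|---|---|---|---|---|
| Nobody leaves | 0.152 | 0.118 (22%) | 0.070 (54%) | -0.222 | -0.135 | -0.189 |
| Unrelated to IgG | 0.146 | 0.108 (26%) | 0.075 (49%) | -0.202 | -0.068 | -0.187 |
| Follows clearance | 0.142 | 0.115 (19%) | 0.111 (22%) | -0.196 | -0.153 | -0.216 |
| Earlier with high IgG | 0.144 | 0.123 (15%) | 0.086 (40%) | -0.201 | -0.323 | -0.161 |
| Earlier with low IgG (discharge or death) | 0.145 | 0.104 (28%) | 0.055 (62%) | -0.213 | +0.194 | -0.174 |
| No effect; unrelated | -0.005 | 0.003 | 0.000 | -0.003 | +0.021 | +0.017 |
| No effect; earlier with high IgG | 0.004 | 0.016 | 0.010 | -0.002 | -0.288 | -0.032 |
| No effect; earlier with low IgG | -0.010 | -0.022 | -0.019 | +0.009 | +0.261 | +0.017 |

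Monte Carlo error on log-duration is about 0.043/√12 = 0.012.

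- CT: attenuated in every setting with a true effect, under both simple rules. With no true effect, every estimate was within 0.022 of zero.
- Duration, uncensored: attenuated in the first three settings, exaggerated in the fourth, wrong sign in the fifth. With no true effect and IgG-dependent leaving, the false effects were 0.288/0.043 = 6.7 and 0.261/0.043 = 6.1 standard errors, against a threshold of 2.97.
- Duration, interval-censored: nearer the truth in all eight settings, though in the null setting with unrelated leaving the gain is within simulation error. Under IgG-dependent leaving it still fell short by 1 - 0.161/0.201 = 20% and 1 - 0.174/0.213 = 18%.

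**Simulation 2 (all inputs assumed).** n = 200, 300 replicates. The true time ratio for high versus low IgG is 0.70, with Weibull clearance (median 7-14 days) and stay with median 9 days, 14 days or unlimited. Between 9% and 72% of patients had no observed clearance. Mean first-negative day among clearers gave 0.85-0.94, last-positive day 0.68-0.86, and an interval-censored Weibull model 0.69-0.71. In a separate CT check (40 replicates), dropping swabs beyond CT 40 cut the slope difference from 0.25 to 0.18, 0.40 to 0.29 and 0.475 to 0.375, that is by 28%, 28% and 21%.

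Neither a Tobit-type mixed model for CT nor a competing-risk model for death was fitted.

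**The case against.** The plan names none of the simple analyses simulated above: not last positive day, not first-negative day among clearers, not dropping negatives, not a fixed CT of 40. It also names no antibody term in these models, so the size of any bias concerns a coefficient that is not yet specified. Both points stand. What is shown is a stated model that cannot deliver duration, and a gap that an analyst would have to fill by choice.

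The positivity part of the endpoint is already usable. A binomial mixed model of positive or negative at each scheduled swab needs neither an exact clearance time nor a CT for negatives, and persistence could be read from its fitted curve. This stands too, with two limits: it still depends on why swabs are missing, and the plan lists duration and CT level as separate quantities.

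The swab grid may be less sparse than the schedule suggests, because footnote g of Section 2.4 tracks routine-care tests. That is possible, but the PCR form has only fixed time slots, so the use of extra results is uncertain.

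Finally, the near-perfect recovery in Simulation 2 comes from fitting a Weibull model to Weibull data, without deaths or IgG-dependent stay. That is fair, and Simulation 1 shows the residual bias.

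**Conclusion.** The mismatch is real. RNA duration is one interval- and right-censored value per patient, death precludes its observation, negative swabs have no CT, and Section 3.1 deals with none of this. An antibody effect on CT level would tend to be attenuated, by 15-28% if negatives are dropped and 22-62% if they are set to CT 40 in the settings tried. Bias in an uncensored duration analysis has no fixed direction. All sizes are illustrative, since every clearance, CT and length-of-stay input is assumed.

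A reader might infer that the plan would understate any antibody effect on clearance. The documents do not support that. The trial's question is whether IgG changes clinical outcome. If it changes discharge or death, an uncensored duration analysis can overstate the effect, create one or reverse it. The planned positivity analysis is also not subject to the two defects of inexact duration and missing CT.

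The point concerns one secondary endpoint in each group. The primary analyses are untouched. It should be corrected before the data are analysed.

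**What to change.** In Section 3.1:

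1. Define duration as time from transfusion to first negative swab. State how to treat a later positive and a patient already negative before transfusion.
2. Analyse it with an interval-censored time-to-clearance model with unit IgG as predictor. Use the last positive and first negative swabs as bounds, and right-censor at the last swab for patients discharged or still positive.
3. Treat death as a competing event, or as never cleared, rather than as ordinary censoring. Add a sensitivity analysis for informative discharge.
4. Include any routine-care PCR results that are tracked, and give the PCR form room for them.
5. Model CT with a censored (Tobit-type) mixed model in which a negative swab is right-censored at the assay's last cycle, with an IgG-by-time term.
6. Keep the binomial mixed model for swab positivity.

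The cost is SAP wording, a small form change and modest extra programming, with no new swabs or visits. The price is a parametric assumption, and some bias remains if discharge depends on IgG.

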#### 3.2 Power and sample size

We determined sample size based on a logistic regression model with a linear relationship between outcome and IgG level, and we used simulations to evaluate power for different sample sizes since we expect some sort of non-linear relationship. We assumed a piecewise model in which the probability of a good outcome increased once IgG levels were greater a threshold. Most of our power calculations used a threshold of 5 since a larger threshold resulted in slightly greater power. We expect this simulation approach to provide an estimate of the minimal power since we use a linear

relationship when the relationship is actually not linear. We assumed the baseline probability was 25% for 28-day survival and 38% for intubation rate. We selected a sample size of 200 for 28-day survival since this sample size provides excellent power (87.8%) for detecting an increase in 28-day survival to 50% (Table 1). We selected a sample size of 300 for intubation rate since this sample size provides excellent power (87.9%) to detect a decrease in intubation rate to 18% (Table 2).

Table 1. Power fo	or detecting an
increase in 28-day s	urvival when the
baseline probability	is 0.25 and the
sample size is 200.	
28-day Survival for	Power
high levels of IgG	
0.45	74.4%
0.50	87.8%

Table 2. Power f	for detecting a
decrease in intubation	on rate when the
baseline probability	is 0.38 and the
sample size is 300.	
Intubation Rate for	Power
Intubation Rate for high levels of IgG	Power
	Power 60.6%
high levels of IgG	

## 4. Protection of Human Subjects

The entirety of this study will be approved and monitored by the Beaumont Health Institutional Review Board of Record (FWA0002516).

This research will be conducted as a clinical investigation requiring an IND as per title 21 of the Code of Federal Regulations, part 312 (21 CFR part 312) and the guidance from the FDA given on May 1, 2020 found at https://www.fda.gov/vaccines-blood-biologics/investigational-new-drug-ind-or-device-exemption-ide-process-cber/recommendations-investigational-covid-19-convalescent-plasma

#### 4.1 Risks to the Subjects

#### **Human Participant Involvement and Characteristics**

Antibody-level Based Analysis of COVID Convalescent Serum, ABACCuS, will be a prospective, single-center, double-blinded, study of the effectiveness of COVID-19 convalescent plasma for the treatment of COVID-19.

We plan to enroll 500 inpatients from the eight Beaumont Hospitals, 300 of which are requiring >6L of oxygen to maintain  $O_2$  saturation >92% but are not requiring intubation and 200 of which are requiring intubation. All enrolled patients, or their legally authorized representative (LAR) must sign an Informed Consent Form (ICF).

All patients will receive a unit of COVID-19 convalescent plasma but the antibody content of the unit will not be known and there will be a double-blind such that neither the patient nor the study personnel will know the anti-SARS-CoV-2 antibody levels within the plasma.

During the study, various clinical and demographic data on each patient will be collected as detailed in the Research Design section.

A schedule of events for all patients in the study is included above (**Section 2.4**). Inclusion and exclusion criteria for the study are included above (**Section 2.3**).

No vulnerable populations of children or pregnant women will be recruited to the study. Children are exempted due to differing impact of SARS-CoV-2 on the pediatric population as compared to that of adults. Pregnant women are exempted due to unknown risks to the fetus. Cognitively impaired patients are allowed but will need to be consented using an LAR.

#### **Sources of Materials**

Participants will provide the required blood samples at the indicated time points, as described in the Research Strategy, and outlined in the above schedule of events (**Section 2.4**). Additional participant data will be obtained through a chart review within Beaumont's EMR (EPIC) and supplemented where appropriate by patient completion of interviews.

All patients enrolled in the study will be followed daily while inpatient by research coordinators who will gather all required data.

#### **Potential Risks**

Historical and current anecdotal data on use of convalescent plasma suggest its use to treat COVID-19 is generally safe. The large number of exposed individuals, in combination with the high mortality of COVID-19, particularly in vulnerable persons, strongly suggests that the potential benefits of convalescent serum outweigh its possible risks in SARS-CoV-2 infected individuals with significant oxygen requirements.

#### **Known Risks of Plasma Transfusion**

Risks of any transfusion of plasma include: fever, chills, rash, headache, serious allergic reactions, TRALI, TACO, transmission of infectious agents.

The chances of any of these occurring are as follows:

Acute hemolytic reaction: 1 in 40,000 units transfused

Febrile transfusion reaction: 1 in 100 to 1 in 1000 units transfused

Urticarial reaction (hives): 1 in 100 units transfused Anaphylaxis: 1 in 20,000 to 1 in 50,000 units transfused

Transfusion related acute lung injury (TRALI): 1 in 1,200 to 1 in 190,000 units transfused

Transfusion related circulatory overload (TACO): less than 1 in 100 units transfused

Transmission of Hepatitis B: less than 1 in 250,000 units transfused Transmission of Hepatitis C: less than 1 in 1,000,000 units transfused

Transmission of HIV: less than 1 in 1,000,000 units transfused

# **Hypothetical Risks of Plasma Transfusion**

There is a theoretical risk of antibody-mediated enhancement of infection (ADE). ADE has been shown to occur for several viral diseases, most notably flaviviruses including Dengue and Zika, and involves an enhancement of disease in the presence of non-neutralizing or poorly neutralizing antibodies. The concern has been raised that the highly variable presentation of COVID-19 may in part be due to an ADE phenomenon due to partially cross-reacting antibodies from other human coronaviruses, most likely OC43 or HKU1 as they, like SARS-CoV-2 are members of the Beta-coronavirus family and are more likely to be cross reactive. Such ADE phenomena have been seen in both SARS and MERS in animal studies so are definitely of concern in COVID-19.

While it would be expected that COVID-19 convalescent plasma would have high titers

of neutralizing antibody against SARS2-CoV-2, this is not always the case and antibody levels can vary. When plasma from donors who only test positive by serology are added into the pool of available COVID convalescent plasma the concern rises further.

Just as low neutralizing antibody levels can potentially cause issue due to ADE, high levels of anti-Spike IgG were found to be directly responsible for increased acute lung injury in a Chinese macaque model of SARS infection. We must be concerned of the danger of both too low and too high a level of neutralizing antibodies in convalescent plasma. The use of COVID convalescent plasma must be carefully studied over a range of antibody levels to be sure it is safe to use at any level. This study is designed to detect any evidence of worsening respiratory status based on actual antibody level in the plasma transfused.

Another theoretical risk is that administering antibody to those with an active SARS-CoV-2 infection may treat the disease but modify the native immune response such that treated individuals mount an attenuated humoral immune response. This would leave them vulnerable to subsequent re-infection. Such a phenomenon has been seen in respiratory syncytial virus where passive antibody treatment before vaccination with respiratory syncytial virus was shown to attenuate humoral but not cellular immunity. This has not been demonstrated in coronaviruses to this point.

# **Risks of Laboratory Testing**

For all patients there will be multiple blood draws. For female patients of childbearing years, a serum pregnancy test will be sent before a unit of plasma is ordered, and if positive they will be removed from the study, whenever possible this test will be added on to previously drawn blood or done at the same time as another blood draw. A blood draw carries the common risks of bleeding, bruising, and pain, and the rare risks of blood clot, infection, light-headedness, dizziness, and fainting.

For all patients there will multiple nasopharyngeal swabs. The risks of a nasopharyngeal swab: local discomfort, vomiting.

